## **7 Study flow and visit schedule**

### **7.1 Study flow and visit schedule**

[Table 7-1](#) to [Table 7-4](#) list all of the assessments and indicate with an "x" where visits are performed. All data obtained from these assessments are recorded in the eCRF.

**Table 7-1 Core Phase - Visit evaluation schedule**

	Category	Protocol Section	Screening	Baseline (first dose)	Study Period											End of Treatment Visit (last dose)	Study Completion Visit ( Last dose + 28 days)		
					3	4	5	6	7	8	9	10	11	777	779				
Visit Number			1	2	3	4	5	6	7	8	9	10	11	777	779				
Study Week			-3 to 0	0	1	2	4	8	13	17	22	26	31	35					
Fasting Blood Glucose	D	7.2.2.5.2	x		x	x	x	x	x	x	x	x	x	x					
HbA1c	D	7.2.2.5.2	x				x		x				x		x				
Midnight salivary cortisol	D	7.2.1.3	x				x	x	x	x	x	x	x	x	x				
Urinary free cortisol and urine creatinine	D	7.2.1.1	x				x	x	x	x	x	x	x	x	x				
Serum cortisol	D	7.2.1.2	x			x	x	x	x	x	x	x	x	x	x				
Plasma ACTH	D	7.2.1.4	x			x	x	x	x	x	x	x	x	x	x				
HbsAg and anti-HCV	D	7.2.2.5.3	x																
Urinalysis	D	7.2.2.5.6	x						x				x	x	x				
Pregnancy Test	D	7.2.2.5.7	x	x	x	x	x	x	x	x	x	x	x	x	x				
Imaging/Other assessments																			
ECG (pasireotide pre-dose)	D	7.2.2.5.9	x	x	x	x	x	x	x	x	x	x	x	x	x				
Echocardiogram	D	7.2.2.5.10		x												x			
Gallbladder Ultrasound	D	7.2.2.5.8	x							x						x			
Safety																			
Adverse events	D	10.3.1.2														Continuous			
Drug administration	D	6														Continuous			

**Table 7-2 Extension Phase - Visit evaluation schedule**

	Category	Protocol Section	Study Period											End of Treatment Visit (last dose)	Study Completion Visit ( Last dose + 28 days)	
			13	14	15	16	17	18	19	20	21	22, 23...				
Visit Number			43	51	59	67	75	83	91	99	107	115, 123...	778	779		
Study Week														Last dose		
Imaging/Other assessments																
ECG (pasireotide pre-dose)	D	7.2.2.5.9	x	x	x	x	x	x	x	x	x	x	x	x		
Echocardiogram	D	7.2.2.5.10			x			x			x	x	x	x	x	
Gallbladder Ultrasound	D	7.2.2.5.8			x			x			x	x	x	x	x	
Safety																
Adverse events	D	10.3.1.2											Continuous			
Drug administration	D	6											Continuous			

Please refer to [Table 7-3](#) for extension phase assessment frequencies.

**Table 7-3 Extension Phase - Assessment frequencies**

Assessment	Frequency
Gallbladder	Every 6 months (24 weeks)
Hematology	Every 4 months (16 weeks)
GH and IGF-1	Every 4 months (16 weeks)
Free T4 and TSH	Every 6 months (24 weeks)
Blood chemistry	Every 4 months (16 weeks)
LFT	Every 2 months (8 weeks)
Coagulation	Every 4 months (16 weeks)
Fasting blood glucose	Every 2 months (8 weeks)
HbA1C	Every 4 months (16 weeks)
Midnight salivary cortisol	Every 2 months (8 weeks)
Urinary free cortisol and urine creatinine	Every 2 months (8 weeks)
Serum cortisol	Every 2 months (8 weeks)
Plasma ACTH	Every 2 months (8 weeks)
Signs and symptoms of Cushing's disease	Every 2 months (8 weeks)
Urinalysis	Every 4 months (16 weeks)
Pregnancy test	At every scheduled visit
ECG	Every 2 months (8 weeks)
Echocardiogram	Every 6 months (24 weeks)

**Table 7-4 Central Laboratory parameters collection plan**

Test Category	Test Name
Hematology	Hematocrit, Hemoglobin, MCH (Mean Corpuscular Hemoglobin), MCHC (Mean Cell Hemoglobin Concentration), MCV (Mean Corpuscular Volume), Platelets, Red blood cells, White blood cells, RBC Morphology with Differential (Basophils, Eosinophils, Lymphocytes, Monocytes, Neutrophils)
Chemistry	Albumin, Alkaline phosphatase, ALT (SGPT), AST (SGOT), GGT, Calcium, Urine Creatinine, Creatine kinase, amylase, lipase, Direct Bilirubin, Indirect Bilirubin, Total Bilirubin, Total Cholesterol, LDL- cholesterol, HDL-cholesterol, Total Protein, Triglycerides, Blood Urea Nitrogen (BUN) or Urea, Uric Acid, magnesium, sodium, potassium, serum creatinine, fasting blood glucose and glycosylated hemoglobin (HbA1C). Estimated glomerular filtration rate from serum creatinine at screening and end of treatment only
Urine collection	24 hour urinary collections for mUFC
Coagulation	International normalized ratio [INR] and Prothrombin time (PT)
Additional hormones	Midnight salivary cortisol, Urine free cortisol (UFC), Insulin-like growth factor 1 (IGF-1), GH, Free T4, and TSH, serum cortisol, Plasma ACTH
Pregnancy and assessments of fertility	All pre-menopausal women who are not surgically sterile will undergo a urine dip-stick - pregnancy test at visits indicated in Table 7-1 through Table 7-4 . The patient will be required to undergo a serum $\beta$ -hCG pregnancy test if the urine dip-stick pregnancy test is positive. A positive serum pregnancy test requires immediate interruption of study treatment until the assessment is confirmed. If positive, the patient must be discontinued from the study.

### **7.1.1 Screening**

The informed consent must be signed prior to ANY screening procedure being performed. Screening visit (Visit 1) should occur within 28 days prior to the baseline visit (Visit 2). The site should enter the Interactive Web Response System (IWRS) when a patient signs the informed consent and begins his/her screening. Patients that do not meet eligibility criteria are allowed to be rescreened and should use the same patient ID number. Rescreening should be documented in the source files.

If the following procedures meet all entry criteria at the original screening they do not have to be repeated for patients who rescreen within 60 days from the first day of the initial screening: vital signs, MRI, and gallbladder ultrasound. Any of these assessments that are abnormal and all other assessments not listed here are to be repeated.

#### **7.1.1.1 Enrollment and eligibility confirmation**

In order to determine and confirm the eligibility of the patient, when all screening procedures are completed, a key eligibility checklist must be completed in IWRS by the investigator or designee prior to receiving the first dose. After the eligibility has been checked and the patient is confirmed as eligible for the trial, the patient can then be enrolled for the trial.

#### **7.1.1.2 Information to be collected on screening failures**

Patients who sign an informed consent but fail to be started on treatment for any reason will be considered a screen failure. The reason for screen fail will be entered on the appropriate CRF page. Screen failed patient's demographic information will still be recorded on the Demography CRF page. No other data will be entered into the clinical database for screen failed patients. Screening assessments of 24 hour urine free cortisol and late night salivary cortisol for patients who are screen failures will be collected by the central laboratory for analysis but no CRF page is to be completed. IWRS must be notified within 2 days of the screen fail.

#### **7.1.1.3 Patient demographics and other baseline characteristics**

Standard demographic information and medical history will be collected. Cushing's disease history and diabetes history together with the medication/treatment used will also be collected. Other baseline assessments will be collected as per [Table 7-1](#) and [Table 7-2](#).

#### **7.1.1.4 Treatment period – core phase**

The Study period in the core phase of the study is 35 weeks. Study visits are at week 1, week 2, week 4, week 8, week 13, week 17, week 22, week 26 week 31 and week 35. All visits should be performed within the indicated week (+/- 1 day).

### **7.1.2 End of treatment, including premature withdrawal and study discontinuation visit**

Patients who discontinue study treatment before visit 777 in the core phase and visit 778 in the extension phase, should be scheduled for a visit as soon as possible, at which time all of the assessments listed for the EOT visit will be performed ([Table 7-1](#) and [Table 7-2](#)). An End of Treatment Phase Disposition CRF page should be completed, giving the date and reason for stopping the study treatment. At a minimum, all patients who discontinue study treatment, including those who refuse to return for a final visit, will be contacted for safety evaluations during the 28 days following the last dose of study treatment.

If a study withdrawal occurs, or if the patient fails to return for visits, the investigator must determine the primary reason for a patient's premature withdrawal from the study and record this information on the End of Treatment Discontinuation CRF page. The investigator must contact IVRS to register the patient's discontinuation.

For criteria for premature withdrawal refer to Section 7.1.2.1.

#### **7.1.2.1 Criteria for premature patient withdrawal**

Patients **may** voluntarily withdraw from the study or be dropped from it at the discretion of the investigator at any time.

Patients **must** be withdrawn from the study if any of the following occurs:

1. Patients experiencing unacceptable drug-related toxicity (as described in [Table 6-1](#))
2. Uncontrolled diabetes mellitus (DM), consistently high capillary glucose values in excess of 275 mg/dL (15.5 mmol/L), FPG  $\geq$  240 mg/dL (13.3 mmol/L) or HbA1c value  $\geq$  10 % despite prior appropriate management and prior dose adjustment of the study drug,
3. Patients experiencing adverse events in QTc:
  - a confirmed QTcF  $>$  480 msec and discontinuation recommended by a cardiologist, or
  - Mean QTcF  $>$  500 msec measured by triplicate ECGs and confirmed by a cardiologist
  - Significant arrhythmia findings from Holter monitoring such as:
    - a. Any ventricular or supra-ventricular tachyarrhythmia associated with symptoms of hemodynamic compromise
    - b. Sustained ventricular tachycardia ( $>$ 30 sec) irrespective of symptoms
    - c. Recurrent non-sustained VT ( $\geq$  3 beats) during any 24-hour monitoring period
    - d. Torsades de Pointes (TdP)
    - e. Cardiac arrest
    - f. Pause  $>$ 5 seconds
    - g. Second or third degree AV block
  - New occurrence of clinically significant/symptomatic bradycardia, or
  - Increased risk of QT prolongation by use of QT prolonging medication, or
  - Hypokalemia ( $<$ 3.5 mmol/L) or hypomagnesaemia ( $<$ 0.7 mmol/L) confirmed by repeat testing that is either a new finding or accompanied by vomiting or diarrhea and not corrected by treatment.

- Evidence of hypoadrenalinism: defined as an early morning (between 8 and 10 am) serum cortisol < 3 µg/dL and a UFC measurement < LLN or symptoms suggestive of hypoadrenalinism (e.g. postural hypotension, nausea, and abdominal pain) in association with a UFC measurement < LLN, which persist after drug dose adjustment
- Lack of efficacy: consistently elevated UFC level and lack of clinical benefit after  $\geq 3$  months treatment
- Pregnancy
- Patient experiencing
  - a. ALT or AST  $> 3 \times$  ULN and Total Bilirubin  $\geq 2 \times$  ULN and ALP  $< 2 \times$  ULN
  - b. ALT or AST  $> 5 \times$  ULN  $\leq 8 \times$  ULN persistent for more than 2 weeks
  - c. ALT or AST  $> 8 \times$  ULN

If any of those 3 discontinuation criteria are met, study medication should be discontinued immediately. In addition, proper safety follow up management should be performed as outline in [Section 6.5.4](#). Re-challenge of study medication is prohibited once discontinuation criteria are met.

If such withdrawal occurs, or if the patient fails to return for visits, the investigator must determine the primary reason for a patient's premature withdrawal from the study and record this information on the Study Completion CRF page. Patients may be withdrawn from the study prematurely for one of the following reasons:

1. Adverse event(s)
2. Abnormal laboratory value(s)
3. Abnormal test procedure result(s)
4. Protocol violation
5. Subject withdrew consent
6. Lost to follow-up
7. Administrative problems
8. Death

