**Figure 6-2 QT Prolongation monitoring flow chart**

#### 6.5.4 Hepatic Safety Management

Patients who develop increased transaminase and/or total bilirubin ( $> 2.0 \times \text{ULN}$ ) levels, should be monitored with a second liver function evaluation for confirmation. If confirmed, liver function should be frequently monitored until values return to pre-treatment levels.

If any of the criteria below are observed at any scheduled or unscheduled visit the sponsor should be notified immediately and the Hepatic Safety evaluation, described below, should be performed preferably within 48- hours of awareness of the abnormality:

Patient experiencing

- ALT or AST  $> 3 \times$  ULN and total bilirubin  $\geq 2 \times$  ULN
- ALT or AST  $> 5 \times$  ULN
- total bilirubin  $> 2.0 \times$  ULN

The following should be performed immediately within 72 hours of awareness of the abnormality:

[figure not shown]
- Perform liver-directed medical history and physical examination (i.e. assess occupational hazards, concomitant medications including OTC meds, inter-current illness, etc.)
- Liver function tests: ALT, AST, total bilirubin, (fractionate to direct/indirect bilirubin if total bilirubin is  $> 2.0 \times$  ULN), Albumin, PT, INR, ALP, and GGT.
- Perform hepatitis screen: anti-HAV, IgM (to confirm acute Hepatitis A), HbsAg, Anti-HBc, anti-HCV (if positive, PCR viral load should be assessed), Anti-HEV, ANA antibodies, anti-smooth muscle anti-bodies, CMV and EBV
- Perform abdominal ultrasound (liver and biliary tree)

[figure not shown]
Liver function tests (LFTs) should be monitored every 3-4 days until resolution or return to baseline status.

Patients should be managed according to the LFT algorithm [Figure 6-3](#). Patients may need to be discontinued if the abnormal liver function criteria are met upon LFT retesting (See discontinuation criteria [Section 7.1.2.1](#)). Progress reports of the event should be maintained until resolution or stabilization (i.e. no further elevation after 2 consecutive assessments).

If any of these criteria are met and not confirmed by repeat testing, and the event is considered to be an adverse event by the investigator, the event must be recorded on the Adverse Event eCRF page; if the event is deemed serious by the investigator, then proceed with completing the SAE form. In addition, any significant findings from the physical examination should be recorded on the Adverse Event eCRF page.

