**Table 6-4 Guidelines for treatment of patients experiencing adverse events**

Patients	Adverse Event	Action
All	AE grade $\leq$ 2 (mild to moderate)	No drug adjustments
	AE grade $\geq$ 3 (severe to life-threatening) and judged as pasireotide-related	Reduce dose of by 0.3mg bid. If AE improves to grade $\leq$ 2 within 1 week, increase dose by 0.3mg bid. If AE recurs at grade $\geq$ 3, reduce dose by 0.3mg bid again and remain at lower dose. If AE does not improve to grade $\leq$ 2 within 1 week on lower dose, reduce dose by 0.3mg bid again if possible. If AE does not improve to grade $\leq$ 2 within 1 week on 0.3mg bid patient should be discontinued from study treatment
	AE grade $\geq$ 3 (severe to life-threatening) and judged as cabergoline-related	Reduce dose from daily schedule to every other day schedule. If AE improves to grade $\leq$ 2 within 1 week, increase dose to daily schedule. If AE recurs at grade $\geq$ 3, reduce dose every other day schedule again and remain at that schedule. If AE does not improve to grade $\leq$ 2 within 1 week on the every other day schedule, patient should be discontinued from study treatment
	All patients	For patients experiencing hyperglycemia, the dose should be reduced if severity grade 3 or greater persists despite appropriate management. If the hyperglycemia is considered to be life-threatening, the patient should be withdrawn from study treatment regardless of anti-diabetes treatment
	AE grade 3 – All patients	NCI-CTCAE v4.03 grades diabetes that is treated with insulin as a grade 3. However, diabetes grade 3 will require a study drug dose reduction only in cases of uncontrolled hyperglycemia despite appropriate management. Patients who despite appropriate therapeutic interventions and dose reduction of study drug, develop uncontrolled diabetes and/or consistently high blood glucose values: FPG $\geq$ 240mg/fdL (13.3 mmol/L) or HbA1c value $\geq$ 10% will require study treatment discontinuation
	Hypocortisolism	If a patient shows high sensitivity to pasireotide 0.6 mg bid resulting in cortisol values $<$ LLN and/or signs/symptoms consistent with the diagnosis of hypocortisolism, the dose of pasireotide can be decreased to 0.3 mg bid. Despite the dose reduction, some patients may still present with cortisol values $<$ LLN and/or signs/symptoms consistent with hypocortisolism; in this case the dose of pasireotide can be further reduced to 0.3 mg qd in order to achieve and maintain normal cortisol levels.

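### For liver criteria (a) and (c), Protocol 7.1.2.1, 6.5.4 and Table 6-4 do not give one consistent stopping rule, and no order of precedence is stated

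*Protocol*

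**What the plan says.** **Protocol 7.1.2.1** lists events for which a patient must "be withdrawn from the study if any of the following occurs". The liver items are:
- (a) ALT or AST above 3 x ULN with total bilirubin at least 2 x ULN and ALP below 2 x ULN;
- (b) ALT or AST above 5 and up to 8 x ULN, "persistent for more than 2 weeks";
- (c) "ALT or AST $> 8 \times$ ULN".

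The text after the list reads "If any of those 3 discontinuation criteria are met, study medication should be discontinued immediately", and then "Re-challenge of study medication is prohibited once discontinuation criteria are met". It sends the reader to 6.5.4 for follow-up only: "proper safety follow up management should be performed as outline in" that section.

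**Protocol 6.5.4** sets triggers for sponsor notification and a liver work-up: ALT or AST above 3 x ULN with bilirubin at least 2 x ULN, ALT or AST above 5 x ULN, or bilirubin above 2 x ULN. It then says "Patients may need to be discontinued if the abnormal liver function criteria are met upon LFT retesting", citing 7.1.2.1. It refers management to the algorithm in Figure 6-3, which is not visible in the text reviewed.

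**Protocol Table 6-4** tells sites, for grade 3 or higher events judged pasireotide-related, to reduce the dose by 0.3 mg bid and, if the event improves to grade 2 or lower "within 1 week, increase dose by 0.3mg bid". The cabergoline row has the same shape: less frequent dosing, then back to daily. Hyperglycemia, hypocortisolism and QT prolongation are handled separately; liver events are not. Section 6.6 calls the table a guideline, but asks for sponsor approval of any departure from it.

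**The concern.** A site with a high transaminase result in hand can open three places in the protocol and find different instructions. One requires a permanent stop and mentions no repeat sample. One speaks of stopping after a retest. One, if the event is graded 3 or higher and attributed to pasireotide, calls for a lower dose with a return to the higher one on improvement. The protocol does not say which governs.

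At stake is a patient's exposure to study drug after a liver signal, which would depend on the passage the site reads. Sites following different passages would also produce discontinuation and dose-adjustment counts that are not comparable, and SAP 6.6.1 tabulates both. Under Protocol 10.2.3, stopping before week 35 counts as non-response, so the site's reading can also reach the primary endpoint.

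**Working it through.** The point concerns consistency of text, and there is no planned figure to reproduce. The check is to take each liver-test situation and read off what each passage requires.

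| Situation | 7.1.2.1 | 6.5.4 | Table 6-4 (if drug-related) | Result |
|---|---|---|---|---|
| ALT/AST > 8 x ULN, first value | (c) met: withdraw, stop at once, no re-challenge | Work-up; possible discontinuation on retest | Grade 3 or higher: reduce, then re-escalate. Grade 2 or lower: no drug adjustment | Conflict |
| ALT/AST > 3 x ULN, bilirubin >= 2 x ULN, ALP < 2 x ULN | (a) met: same action | Work-up; possible discontinuation on retest | Grade 3 or higher: reduce, then re-escalate | Retest conflict with 6.5.4; re-escalation conflict if graded 3 or higher |
| ALT/AST > 5 to 8 x ULN, first value | (b) not yet met | Work-up, repeat tests every 3-4 days | May prompt a dose change; 7.1.2.1 does not forbid it until (b) is met | No conflict between 7.1.2.1 and 6.5.4 |
| Bilirubin > 2 x ULN alone, or ALT/AST > 3 to 5 x ULN with bilirubin >= 2 x ULN and ALP >= 2 x ULN | None of (a)-(c) met | Work-up trigger only | General row if grade 3 or higher | No conflict between 7.1.2.1 and 6.5.4 |

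Four further steps:

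1. **Retest.** Other items in the 7.1.2.1 list state a confirmation condition: (b) requires persistence, low potassium or magnesium requires repeat testing, and mean QTcF above 500 msec requires a cardiologist. Items (a) and (c) state none, so on their face they act on one value. Section 6.5.4 ties discontinuation to retesting, and for triggers not confirmed on repeat it describes event recording and mentions no stop.

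2. **Re-escalation.** This conflict does not depend on the retest. Under 6.5.4, a confirmed abnormality with no other cause is a serious adverse event reported as potential drug-induced liver injury. If it is judged pasireotide-related and graded 3 or higher, the general row of Table 6-4 applies on its terms, while 7.1.2.1 prohibits re-challenge once (a) or (c) is met.

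3. **Grade.** The documents do not give the CTCAE grade of an ALT multiple. For a drug-related event under (c) the outcome differs from 7.1.2.1 either way: reduce and re-escalate at grade 3 or higher, no adjustment at grade 2 or lower.

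4. **Precedence.** None is stated. Item 1 of the 7.1.2.1 list refers to Table 6-1 for drug-related toxicity, but Table 6-1 is the dose and schedule table. The one link from the withdrawal list to a toxicity table therefore does not resolve the matter.

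**The case against.** **Section 6.5.4 is not a rival rule.** A reader might infer that it makes liver stopping optional. The documents do not support that. Its triggers are wider than (a) to (c), so many patients who enter the work-up meet no withdrawal criterion, and the sentence with the word may points to 7.1.2.1. It can fairly be read as depending on that section. What remains is the retest condition for (a) and (c), and Figure 6-3 might settle it. This part of the objection stands.

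**Opposite actions for any raised ALT.** A reader might infer this too. It fails for a first ALT or AST above 5 to 8 x ULN, where (b) itself requires more than two weeks of persistence and fits repeat testing every 3-4 days.

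**Table 6-4 is a general guideline.** Section 6.6 allows reduction or withdrawal, and a specific mandatory rule would naturally be read as overriding a general one. The table also applies only once the result counts as an adverse event, is attributed to study drug and is graded. That is a reasonable reading, but nothing states it. Section 6.6 expects sponsor approval for departures, and QT is carved out while liver is not.

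**Primary endpoint.** A reader might infer a shift of several points in the week-35 rate. With 64 patients, one changed classification moves the rate by 1/64 = 1.6 points, but only if that patient would otherwise have responded. At the assumed 34% response, the expected shift is 0.34 x 1.6 = about 0.5 points per patient, against a stated precision of 12.8 points. The number of such patients is not given, and Amendment 4 says first core-phase results were already available. The objection stands in full on this point.

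**Conclusion.** The inconsistency is real for criteria (a) and (c) and limited to them. A site cannot follow both 7.1.2.1 and the general rows of Table 6-4 for a drug-related ALT or AST above 8 x ULN. For an event meeting (a), the re-escalation conflict holds if the event is graded 3 or higher, which is an assumption. Between 7.1.2.1 and 6.5.4 the conflict is narrower: whether a retest comes before the stop. That part is conditional on Figure 6-3, which was not visible; Table 6-4's lack of any liver exemption or pointer is not.

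The case rests on patient safety and uniform conduct. No size can be put on the effect on the week-35 rate from these documents. No view is taken on which of the rules is clinically right. The change is worth making, because the conflict is specific and the repair is small.

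**What to change.** Reconcile 7.1.2.1, 6.5.4 (with Figure 6-3) and Table 6-4 so that they state one rule on two points:

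1. whether criteria (a) and (c) act on the first value or only after a retest;
2. whether, and how, the reduce and re-escalate step in Table 6-4 applies to events meeting 7.1.2.1 (a) to (c).

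State the rule once, add a liver cross-reference in Table 6-4 as is done for QT, and correct the reference to Table 6-1 in item 1 of the 7.1.2.1 list. The sponsor's clinical and hepatic safety team decides which rule stands.

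The cost is amendment wording and one table row. No new assessments are needed, since 6.5.4 already requires repeat liver tests every 3-4 days. SAP section 4 gives 30 June 2019 as the final cut-off and last patient visit. If conduct has ended, the equivalent step is to list in the study report each patient who met (a) to (c), with the action taken and its timing relative to any retest.
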